### 5. PATIENT SELECTION

#### 5.1 Inclusion criteria

1.  $\geq 18$  years of age at the time of study enrollment
2. Biopsy-confirmed primary or metastatic carcinoma with involvement of the lung, liver, adrenal gland, pancreas, kidney, and/or abdominal/pelvic lymph node that would receive SABR
3. Any lesion that would receive SABR is no larger than 5 cm in greatest dimension
4. 1-10 total lesions that would receive SABR
5. If multiple lesions are treated, they must be at least 3 cm apart
6. Eastern Cooperative Oncology Group (ECOG) performance status of 0-2
7. Life expectancy at least 6 months
8. Women of childbearing potential and men must agree to use adequate contraception (hormonal or barrier method of birth control) prior to study entry and for the duration of study participation. Abstinence is acceptable if preferred by patient. Should a woman become pregnant or suspect she is pregnant while participating in this study, she must inform her treating physician immediately.

9. Patients receiving hormonal therapy or immunotherapy such as immune checkpoint inhibitor that had begun at least 4 weeks prior to SABR will be allowed.

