## 8.3 After Study Therapy Completion

After completion of SABR, an optional visit at 6 weeks (+/-14 days), can be performed as per treating physician criteria.

The following will be assessed every three (3) months until 12 month (+/- 28 days) after completion of SABR.

- Physical Examination
- ECOG Performance Status
- CBC
- CMP
- Imaging: CT scan of the chest, abdomen, and pelvis (IV and/or oral contrast as per physician discretion)
- RECIST 1.1
- Adverse Events / SAE
- Concomitant Medications
- FACT-G Survey

Assessments completed as part of the standard of care visits can be used for after treatment visits as long as the test/procedure meets the protocol-required timelines. Note that source documents must identify the standard of care tests/procedures used for this visit and must be reviewed by the investigator for clinical significance. FACT-G and RECIST 1.1, concomitant medications and adverse events evaluation must be performed by a delegated study team member.

**Remote visits:** In the case when an in-person clinic visit is not possible, remote visits will be allowed only for “After Study Therapy” completion visits. When a remote visit occurs, all research specific assessments including the FACT-G questionnaire, concomitant medications, and adverse events will be collected by a delegated study team member.

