## 9.3 Definitions of Disease Response

Definition of response in target lesions:

- **Complete Response (CR):** Disappearance of all target lesions
- **Partial Response (PR):** At least a 30% decrease in the sum of the diameters of target lesions, taking as reference the baseline sum diameters
- **Local Progressive Disease (LPD):** At least a 20% increase in the sum of the diameters of target lesions compared to baseline sum of target lesions, taking as reference the smallest sum on study (this includes the baseline sum if that is the smallest on study). The sum must also demonstrate an absolute increase of at least 5 mm in addition to the relative increase of 20%.
- **Distant Progressive Disease (DPD):** The appearance of at least 1 new lesion.
- **Stable Disease (SD):** Neither sufficient decrease to qualify as a PR or sufficient increase to qualify as PD, taking as reference the smallest sum diameters while on study.

Definition of response in non-target lesions:

- **Complete Response (CR):** Disappearance of all target lesions
- **Progressive Disease (PD):** Appearance of one or more new lesions and/or unequivocal progression of existing non-target lesions
- **Incomplete Response/Stable Disease (SD):** Persistence of one or more non-target lesions

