## 12. PATIENT DISCONTINUATION AND REPLACEMENT

### 12.1 Patient discontinuation

Permanent withdrawal of a patient from the study will occur when any of the following occur pertaining to the subject in question:

- Patient withdraws consent or is lost to follow-up.
- Patient becomes pregnant or has the intent to become pregnant.
- Patient is non-compliant with requirements of this study (i.e., refusal to adhere to scheduled visits) that in the opinion of the investigator warrants study withdrawal.
- AE occurs that in the opinion of the investigator is a contraindication to further treatment on study.
- Study closure.
- Death

If a patient is thought to be lost to follow-up, at least 3 documented attempts must be made to contact the patient before deemed lost to follow up. Any subject that is permanently discontinued from study participation will still be followed for safety and will also continue to have protocol-specified follow up evaluation, unless the subject withdraws consent, is lost to follow-up or enrolled in another clinical study.

Subjects who do not return to the treating institution for evaluations required by the study protocol will be offered telephone follow up every 3 months.

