#### 13.3 Secondary objectives

1-year local control (LC) will be assessed according to RECIST 1.1 criteria and will be estimated using the Kaplan-Meier method along with the corresponding 95% confidence interval from the time of study treatment

1-year overall survival (OS) will be estimated using the Kaplan-Meier method along with the corresponding 95% confidence interval from the time of study treatment

The proportion of patients who experience acute grade 3 or higher toxicity attributable to SABR will be determined along with the corresponding 95% confidence interval. For patients receiving SABR to multiple lesions, acute toxicity will be determined from the date of the initiation of SABR.

Patient-reported quality of life will be determined using the FACT-G survey instrument prior to and after SABR.

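### The plan does not say how deaths are handled in the Kaplan-Meier estimate of 1-year local control; if they are censored, the result is net control and overstates the proportion of patients who fail locally

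*Combined protocol and SAP*

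**What the plan says.** Section 13.3 and the matching part of the protocol summary give the whole analysis of this endpoint: "1-year local control (LC) will be assessed according to RECIST 1.1 criteria and will be estimated using the Kaplan-Meier method". Time runs from study treatment, and a 95% interval is planned. Neither place gives a censoring rule, and cumulative incidence is not mentioned anywhere in the document.

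The event comes from section 9.3, where local progressive disease is "At least a 20% increase in the sum of the diameters of target lesions compared to baseline sum of target lesions", with a further absolute-increase condition. Death is not part of it. Survival is analysed separately: "1-year overall survival (OS) will be estimated using the Kaplan-Meier method".

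Death is listed in section 12.1 ("Permanent withdrawal of a patient from the study will occur when any of the following occur"), but only as a reason for leaving the study. No analysis rule is attached to it.

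On the population, section 5.1 requires "Life expectancy at least 6 months" and admits "Biopsy-confirmed primary or metastatic carcinoma with involvement of the lung, liver, adrenal gland, pancreas, kidney" and abdominal or pelvic nodes, with ECOG performance status 0-2. Section 8.3 sets the follow-up: "The following will be assessed every three (3) months until 12 month (+/- 28 days) after completion of SABR".

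**The concern.** A patient who dies without local progression can no longer progress locally. Kaplan-Meier with that death censored treats the patient as though local failure could still be observed later, and spreads the patient's weight over those still under follow-up. The curve then describes net local control, meaning control in a setting where nobody dies first. That reading needs death and local failure to be independent. This is doubtful here, because extent of disease and tumour biology may drive both in a mixed population of primary and metastatic tumours.

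A reader is likely to take a 1-year local control figure as the share of treated patients whose lesions stayed controlled. One minus the censored Kaplan-Meier estimate is larger than the share who in fact failed locally. The minimum life expectancy is half the 12-month horizon, so the two quantities may differ.

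The silence also leaves a choice open until the data are in. Censoring deaths, treating them as competing events and counting them as failures give three different quantities, all of which could be reported under the same endpoint name.

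**Working it through.** **Inputs.** From the documents: n = 30 (section 13.4), a 1-year horizon, Kaplan-Meier with a 95% interval (section 13.3), and an event that excludes death (section 9.3). The documents state no local control rate and no mortality rate, so there is no figure of the plan's own to reproduce. Assumed: net 1-year local failure F of 5% to 30%, 1-year mortality D of 5% to 50%, and constant, independent hazards over the year.

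**Direction.** At each local failure, Kaplan-Meier with deaths censored adds (probability of no local failure so far) × (failures / number at risk) to the failure estimate. The Aalen-Johansen estimate adds (probability of being alive and without local failure so far) × (the same fraction). The second probability is never larger than the first, and it is smaller once a death has occurred. One minus Kaplan-Meier is therefore at least as large as the cumulative incidence in any data set, and larger whenever a death precedes a later local failure.

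**Size.** With hazards a = −ln(1 − F) for local failure and b = −ln(1 − D) for death,

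cumulative incidence at 1 year = a/(a + b) × [1 − (1 − F)(1 − D)].

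- F = 10%, D = 30%: a = 0.1054, b = 0.3567; 0.1054/0.4620 × (1 − 0.63) = 0.228 × 0.37 = 8.4%.
- F = 20%, D = 30%: a = 0.2231, b = 0.3567; 0.2231/0.5798 × (1 − 0.56) = 0.385 × 0.44 = 16.9%.
- F = 30%, D = 50%: a = 0.3567, b = 0.6931; 0.3567/1.0498 × (1 − 0.35) = 0.340 × 0.65 = 22.1%.

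Cumulative incidence by assumed mortality:

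| Net failure (1 − KM) | D = 10% | D = 20% | D = 30% | D = 50% |
|---|---|---|---|---|
| 5% | 4.8% | 4.5% | 4.2% | 3.6% |
| 10% | 9.5% | 9.0% | 8.4% | 7.3% |
| 20% | 19.0% | 18.0% | 16.9% | 14.6% |
| 30% | 28.6% | 27.1% | 25.5% | 22.1% |

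Over the whole grid the excess runs from 0.1 points (F = 5%, D = 5%) to 7.9 points (F = 30%, D = 50%). In patients, at D = 30% the expected number with local failure among 30 is 30 × 0.0844 = 2.5 where F = 10% suggests 3.0, and 30 × 0.169 = 5.1 where F = 20% suggests 6.0.

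**Against sampling error.** Simulation of 10,000 trials of 30 patients per scenario gave these standard deviations (SD) of one minus Kaplan-Meier:

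| F, D | Gap (points) | SD (points) |
|---|---|---|
| 10%, 10% | 0.5 | 5.7 |
| 10%, 30% | 1.6 | 6.0 |
| 10%, 50% | 2.7 | 6.7 |
| 20%, 30% | 3.1 | 8.1 |
| 20%, 50% | 5.4 | 8.9 |

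The gap is below one SD in each. The extreme corner (30%, 50%) was not simulated. With no censoring at all, the SD there would be √(0.3 × 0.7/30) = 8.4 points, already more than the 7.9-point gap, and censoring would be expected to widen it.

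**Why the rule must be written down.** At F = 10% and D = 30%, local control is 90% with deaths censored and 100 − 8.4 = 91.6% on the cumulative-incidence scale. If deaths were counted as failures, the figure would be 0.9 × 0.7 = 63%, which is survival free of local failure.

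**The case against.** The strongest reply is that nothing is being estimated wrongly. If death is independent of local failure, Kaplan-Meier with deaths censored is a valid estimator of net local control, which is a legitimate quantity. Cumulative incidence answers another question. This stands. The defect is that the plan does not say which quantity it wants, and nothing in the documents supports the independence that the net reading needs.

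A second reply is that the gap is small, lies within sampling error at n = 30 and is conservative, since it lowers the reported local control. Overall survival is reported alongside. All of this stands and limits the weight of the point. But the gap always runs in one direction, and a confidence interval for net failure does not account for it.

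Several stronger readings are tempting, and the documents do not support them:

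- That the plan censors deaths. No section says so. It is an inference from the definition in section 9.3 and the separate survival analysis.
- That deaths will be common. A 6-month life expectancy is a minimum for entry, not a forecast, and eligibility also covers primary tumours and ECOG 0-2. No mortality rate is given.
- That the Kaplan-Meier figure itself grows with the number of deaths. Under independent hazards, net failure stays fixed in each row of the table while the cumulative incidence falls. Deaths then affect only the precision of Kaplan-Meier. Dependence between death and local failure could bias it, but that was not modelled here.
- That the decision to go on to phase II/III rests on local control. Section 13.4 lists only toxicity and feasibility criteria.

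**Conclusion.** The point holds as a gap in specification. The plan estimates 1-year local control by Kaplan-Meier without saying how death without local progression is handled. If deaths are censored, the complement of the estimate is net local failure, interpretable as such only under independence, and it exceeds the proportion of patients who actually fail locally.

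The direction is certain once deaths are censored and some precede later local failures. The size is not known. The range of about 0.1 to 8 points rests on assumed failure and mortality rates and on constant independent hazards. Most of that range is a few points or less, and the top is reached only with both rates at their assumed maximum.

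A reader might infer that the planned analysis flatters the treatment or puts the trial's main conclusions at risk. It does neither. Local control would look lower, and it is a descriptive secondary endpoint with no threshold and no part in the sample size or the criteria to advance. The right label is a cheap improvement.

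**What to change.** In section 13.3 and the protocol summary, state that death without prior local failure is a competing event. Report the 1-year cumulative incidence of local failure (Aalen-Johansen) from study treatment, with its 95% confidence interval. Keep the Kaplan-Meier estimate beside it, labelled as net local control with deaths censored, for comparison with published series.

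The cost is a few sentences and a few lines of code. Imaging follow-up and survival are already planned, so no visit, data item or sample size changes. The downside is one more estimate to explain, and the report must make clear that the two figures answer different questions.

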### 13.4 Sample size determination

For this study, a sample size 30 is assessed pragmatically and not based on hypothesis testing. Table 1 shows 90% and 95% confidence intervals for different feasibility rates.

Sample size	Feasible cases	Feasibility rate	90% CI	95% CI
30	27	90%	76% - 97%	73% - 98%
30	24	80%	64% - 91%	61% - 91%
30	21	70%	53% - 83%	51% - 85%

Following criteria will be implemented for this feasibility study to advance to a phase II/III trial:

1. Grade  $\geq 3$  toxicity in no greater than 4 out of 30 patients
2. No grade 5 toxicity
3. Treatment feasibility rate of at least 80%

With a sample size of 30, if the true underlying grade 3 toxicity rate is 10.5%, the probability of no greater than 15% of patients in the sample (maximum 4 out of 30) suffering a grade 3 or higher acute toxicity is 80%. In other words, if the true underlying grade 3 toxicity rate is 10.5%, the probability of satisfying the specified tolerability threshold for escalation to a phase II/III trial is 80%. If the true underlying grade 3 toxicity rate is 21.4%, the probability of no greater than 15% of patients (maximum 4 out of 30) should suffer a grade 3 or higher acute toxicity is 20%. In other words, if the true underlying grade 3 toxicity rate is 21.4%, the probability of satisfying the specified tolerability threshold for escalation to a phase II/III trial is 20%.

With a sample size of 30, if the true underlying feasibility rate is 83.9%, the probability of at least 24 out of 30 patients satisfying the feasibility criteria is 80%. In other words, if the true underlying feasibility rate is 83.9%, the probability of satisfying the specified feasibility threshold for escalation to a phase II/III trial is 80%. If the true underlying feasibility rate is 71.3%, the probability of at least 24 out of 30 patients satisfying the feasibility criteria is 20%. In other words, if the true underlying feasibility rate is 71.3%, the probability of satisfying the feasibility tolerability threshold for escalation to a phase II/III trial is 20%.

### 13.5 Accrual and study duration

It is anticipated that approximately 30 patients will be enrolled and treated in this study. The expected accrual is an average of 1 patient at each participating site per month and a total of 2 patients per month across all participating sites. We expect study accrual to be completed in 15 months.

## 14. ETHICAL AND REGULATORY REQUIREMENTS

### 14.1 Ethical conduct of the study

The study will be performed in accordance with ethical principles that have their origin in the Declaration of Helsinki and are consistent with ICH/Good Clinical Practice, and applicable regulatory requirements.

Study procedures may begin once IRB approval is secured and other details (e.g., study supplies, clinical trial agreements) are in place.

### 14.2 Informed consent

All subjects must sign informed consent to participate in and register for this study. Investigators or their authorized designees will be responsible for obtaining informed consent and authorization to use and disclose protected health information prior to conduct any study-specific procedures.

All subjects will be informed about the following:

- Study aims
- Possible adverse effects
- Study procedures
- Confidentiality of patient data
- Medical records potentially being reviewed by authorized individuals other than the treating physician

Patients should be given the opportunity to ask questions and be allowed time to review the information provided. It will be explained to each patient that participation is voluntary and that subjects have the right to refuse participation at any time during the study. If any patient refuses to participate in this study, it will not affect the patient's subsequent care quality.

The written informed consent must be signed and personally dated by the subject or the subject's legally acceptable representative and investigator.

The Principal Investigator(s) must maintain the original, signed ICF. A copy of the signed document must be given to the patient.

## 15. DATA MANAGEMENT

The Miami Cancer Institute (MCI) Multisite Research Program will be responsible for all data management.

The trial will use Advarra Electronic Data Capture (EDC) system for all data collection. A web-based training for all eCRF users will be provided by MCI Multi-site research office.

All data entered must be verifiable by source documentation or any discrepancy should be explained, and corrections should be dated, initialed and explained (if necessary) and should not obscure the original entry.

Principal investigators are responsible for the accuracy, completeness, legibility and timelines of data reported to coordinating center in the eCRF/EDC and all required reports.

#### 15.1 MONITORING, AUDITING AND QUALITY ASSURANCE

Routine monitoring or audit activities for this study will be conducted by the MCI OCR Office of Research Integrity authorized personnel in accordance with current FDA Regulations, ICH GCP guidelines, site's Standard Operating Procedures (SOPs), IRB and the respective local and national government regulations. The general scope of such visits would be to inspect study data including but not limited to, regulatory requirements, source documentation, original medical records/files and eCRF completion, as applicable, following a risk-based monitoring approach.

The study will be monitored based on procedures established in the Risk-Based Monitoring Plan at the time of protocol activation. A series of monitoring forms, tools and templates including:

MCI Clinical Research Monitoring/Audit Deficiencies Guidance and Summary

Monitoring Letters are utilized to ensure standard and consistent monitoring practices. The monitoring frequency may also be adjusted as per the monitor's discretion based on accrual rate, trial complexity, major deficiency findings, visit rating and safety reporting.

To ensure compliance with current federal regulations and the ICH GCP guidelines, data generated by this study must be available for inspection upon request by representatives of the FDA, national and local health authorities, and duly authorized representatives of any entity providing support for this trial.

